To assess efficacy of treatments for pain relief as measured by POM on Days 3 and 8	Change from baseline of POM on VAS on Day 3 and Day 8 of treatment assessed by 100 mm VAS scale
To assess efficacy of treatments for inflammation of the affected ankle as measured by pressure algometry on Days 3, 5, and 8	Change from baseline in tenderness as measured by pressure algometry on Days 3,5, and 8
To assess efficacy of treatments for inflammation of the affected ankle as measured by pressure algometry on Days 3, 5, and 8	Difference between measurement in affected ankle and contralateral ankle on Days 3,5,and 8
To assess efficacy of treatments for ankle joint function as measured on the Karlsson Scoring Scale	Change from baseline in Ankle Joint Function (Karlsson Scoring Scale) on Days 3,5, and 8

Objectives and Endpoints

To assess efficacy of treatments for swelling of affected ankle as measured by Figure of Eight Method	Change from baseline in circumference of affected ankle as measured by Figure of Eight method on Days 3,5, and 8	
To assess efficacy of treatments for swelling of affected ankle as measured by Figure of Eight method	Difference between circumference of affected ankle to unaffected ankle by Figure of Eight method on Days 3, 5, and 8	
To assess efficacy of treatments for effect on pain intensity as measured by Sum of Pain Intensity Difference (SPID)	SPID from 0 – 24 hours post first dose (Day 1) and from 96 – 120 hours post first dose (Day 5)	
To assess effect of treatments for effect on pain relief as measured by Total Pain Relief (TOTPAR)	TOTPAR from 0 – 24 hours post first dose (Day 1) and from 96 – 120 hours post first dose (Day 5)	
To assess the use of rescue medication among subjects	Number of tablets used to treat ankle pain and overall	
To assess the use of rescue medication among subjects	Number of days on which rescue medication was used to treat ankle pain and overall	

Study Design

This is a Phase III, randomized, double blind, multi-center, active controlled, 2 treatment arm, parallel group, non-inferiority study to evaluate the efficacy and safety of diclofenac diethylamine 2.32% gel applied twice daily versus diclofenac diethylamine 1.16% gel applied four times daily for 1 week in subjects with acute ankle sprain.

To qualify, subjects must experience an acute Grade I -II sprain of the ankle within the past 24 hours. Subjects should be randomized as soon as possible after the injury.

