5.2 Inclusion Criteria

An individual must meet all of the following inclusion criteria to be eligible for enrollment into the study:

- 1. Subject provision of a signed and dated informed consent document indicating that the subject has been informed of all pertinent aspects of the study before any assessment is performed.
- 2. Subject is male or female who, at the time of screening, is between the ages of 18 and 75 years, inclusive.
- 3. A subject who is willing and able to comply with scheduled visits, treatment plan and other study procedures.
- 4. Acute sprain of the lateral ankle on one side only, Grade I-II [Wolfe 2001]
- 5. Pain-on-movement \geq 50 mm on a 100 mm VAS
- 6. Injury within the past 24 hours before randomization
- 7. No pain medication may have been taken within the 24 hours that precedes randomization. Treatment by rest, ice, compression, or elevation (RICE) is authorized prior to randomization. Stable daily doses of acetylsalicylic acid (≤ 162 mg) taken for at least 30 days prior to the first dose of study medication for non-analgesic reasons may be continued for the duration of the study.
- 8. A subject in good general and mental health with, in the opinion of the investigator or medically qualified designee with no clinically significant/relevant abnormalities in medical history or upon physical examination, or condition, that would impact the subject's safety, wellbeing or the outcome of the study, if they were to participate in the study, or affect the individual's ability to understand and follow study procedures and requirements.
- 9. Female subject of childbearing potential and at risk for pregnancy must agree to use a highly effective method of contraception throughout the study and for 14 days after the last dose of assigned treatment. A female subject who is of childbearing potential must meet requirements in Section 5.5.4.

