12.2.5 Primary Analysis(es)

The primary efficacy endpoint will be change from baseline in POM on Day 5 of treatment as assessed by a 100 mm VAS scale.

The following primary non-inferiority hypothesis will be tested for DDEA 2.32% vs DDEA 1.16%:

The null hypothesis is Diclofenac 2.32% DDEA Gel administered BID is inferior to Diclofenac 1.16% DDEA gel administered QID with the alternative hypothesis being Diclofenac 2.32% DDEA Gel administered BID is non-inferior to Diclofenac 1.16% DDEA gel administered QID.

Diclofenac 2.32% DDEA Gel administered BID will be declared non-inferior to Diclofenac 1.16% DDEA gel administered QID if the upper limit of the two-sided 95% confidence interval of the difference between their mean changes from baseline VAS POM responses is less than the established margin of 13 mm.

The primary analysis will be based on an analysis of covariance (ANCOVA) with treatment and center as factors and baseline value as a covariate to estimate the treatment difference twosided 95% confidence interval for the primary endpoint to assess non-inferiority, using the per protocol and mITT analysis populations.

Evidence of a treatment-by-center interaction will be assessed by adding a factor for this interaction in a separate additional analysis model of the primary endpoint. If there is evidence of an interaction (p<0.05), then the primary endpoint outcome will also be summarized by center for further investigation and assessment

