#### 4.3.1 Demographic Characteristics

Categorical demographic variables include gender (Male, Female), race (American Indian or Alaska Native, Asian, Black or African American, Native Hawaiian or Other Pacific Islander, White). These variables will be summarized by the number and percentage of subjects with each relevant characteristic in each treatment group.

Body Mass Index (BMI) will be calculated as weight  $(kg)/[height (m)]^2$ . Age in years, weight in kg, height in cm and BMI in kg/m^2 will be summarized by the mean, standard deviation, median, minimum and maximum values in each treatment group.

All the demographic related information will be taken from Demographic CRF page. Other baseline characteristics information will be taken from the corresponding CRF page for the baseline visits.

Examination on Ankle sprain will be taken from the Examination of Ankle Sprain/Diagnostic Testing for Ankle CRF page.

All demographic information will also be tabulated for ITT, mITT and SAF populations in **PPD**.

Demographic variables will be listed in PPD us

using ITT population.

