#### 4.5.1.2 Statistical Hypothesis, Model, and Method of Analysis

The hypothesis of the study is stated below:

H0: The Diclofenac 2.32% DDEA Gel administered BID is inferior to Diclofenac1.16% DDEA gel administered QID.

 $\mu_T \text{-} \mu_S \geq \delta$ 

Where,  $\mu_S$  is the mean for a standard therapy (Diclofenac 1.16% DDEA Gel administered QID) and  $\mu$ T is the mean for test therapy (Diclofenac 2.32% DDEA Gel administered BID).  $\delta$  is the non-inferiority margin of 13 mm.

H1: Diclofenac 2.32% DDEA Gel administered BID is non-inferior to Diclofenac 1.16% DDEA gel administered QID.

 $\mu_T \text{ - } \mu_s < \delta$ 

 $\delta = 13 \text{mm}$ 

The primary efficacy analysis will be performed on PP population without imputation of missing data. The primary endpoint (Change from baseline in POM ) will be analysed using

GlaxoSmithKline Consumer Healthcare Confidential

Page **19** of **36** 

211206

Statistical Reporting and Analysis plan Draft V2.0 20JAN2021

Analysis of Covariance (ANCOVA) model with treatment and center as factors and baseline POM as covariate.

Diclofenac 2.32% DDEA Gel administered BID will be declared non-inferior to Diclofenac 1.16% DDEA gel administered QID if the upper limit of the two-sided 95% confidence interval of the difference between their mean changes from baseline VAS POM responses is less than the established margin of 13 mm.

Refer sample SAS code in APPENDIX 4.

Assumptions of normality and homogeneity of variances in the ANCOVA model will be evaluated after study un-blinding. If violations are observed then the following will be performed as a post-hoc sensitivity analysis and results will be compared with primary analysis results:

- 1. Suitable data transformations will be tried to achieve the assumptions.
- 2. If suitable transformations cannot be found, then the non-parametric Van Elteren tests will be performed using center as strata. Two sided 95% CI and p value will be presented.

POM by 100 mm VAS analogue scale (CRF page: Pain on Movement ; variable VASSCRL)will be summarized over time (**PPD**) using mITT population. Also POM by 100 mmVAS analogue scale will be summerarized over time by center using mITT population (**PPD**). Above tables (**PPD**) will be repeated for the PP population. POM by 100 mm VAS analogue scale for COVID 19 patients if any will be summarized in **PPD** using mITT population.

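### Sprain grade (I or II), assessed before randomization, is left out of the primary ANCOVA; adding it would be a low-cost improvement to a model that is already valid

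*Protocol*

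**What the plan says.** **Entry.** The Study Design part of the Protocol Summary states: "To qualify, subjects must experience an acute Grade I -II sprain of the ankle within the past 24 hours". Protocol 5.2 requires "Acute sprain of the lateral ankle on one side only, Grade I-II", with injury no more than 24 hours before randomization and baseline POM of at least 50 mm on the VAS. Protocol 5.1 makes the investigator responsible for assessing grade.

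**Randomization.** Protocol 6.5 stratifies by center only.

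**Primary model.** Protocol 12.2.5 specifies an "analysis of covariance (ANCOVA) with treatment and center as factors and baseline value as a covariate", on the per-protocol (PP) and mITT sets. SAP 4.5.1.2 specifies the same terms ("Analysis of Covariance (ANCOVA) model with treatment and center as factors and baseline POM as covariate") and adds that "The primary efficacy analysis will be performed on PP population without imputation of missing data".

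**Other models.** The supportive analyses in SAP 4.5.1.3 change the population, the handling of missing data, the compliance cut-off or the repeated-measures structure, or add a treatment-by-center term. None adds grade or time since injury. The imputation model in SAP 4.5.3 uses the primary-model variables plus the Day 3 value.

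**Baseline tables.** SAP 4.3.3 names POM, tenderness, ankle joint function and swelling as the tabulated disease characteristics. SAP 4.3.1 adds: "Examination on Ankle sprain will be taken from the Examination of Ankle Sprain/Diagnostic Testing for Ankle CRF page". It does not list the fields on that page.

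**The concern.** Grade is a pre-randomization measure of injury severity. Baseline POM also measures severity, but perhaps not all of it. Subjects enter with a score of at least 50 mm, taken at any point up to 24 hours after injury and possibly after rest, ice, compression or elevation, which protocol 5.2 permits before randomization. Two subjects with the same score may have different injuries and recover differently by Day 5.

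Two things would be at stake.

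- **Precision.** The verdict depends on whether the upper 95% limit falls below 13 mm. A covariate that explains residual variance narrows that interval without more subjects.
- **Balance in the PP set.** PP membership depends on compliance, prohibited medication and other deviations, all after randomization. Randomization therefore does not guarantee that the PP arms have the same grade mix. Baseline POM adjusts for part of any difference, and the remainder would pass into the treatment estimate.

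**Working it through.** **Inputs from the documents** (protocol 12.1, SAP 1.4): margin 13 mm, SD 22 mm, assumed true difference 5 mm in favor of DDEA 1.16%, two-sided 95% CI, 120 evaluable per arm, 300 randomized.

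**Inputs that are assumptions.** These are the extra variance explained (R²) by grade, with hours since injury if used; the Day 5 difference between grades; and the grade imbalance between PP arms. The documents give none of them. The 22 mm is taken as the residual SD of the planned model.

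**1. The plan's own figure.** The distance from the assumed difference to the margin is 13 − 5 = 8 mm.

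- n per arm = 2 × 22² × (1.960 + 0.842)² / 8² = 118.7, rounded up to 119. The plan states 120.
- SE = 22 × √(2/120) = 2.84 mm.
- Power at 120 per arm is 80.4% by normal approximation and 80.1% by noncentral t with 238 degrees of freedom.
- 120 / (1 − 0.20) = 150 per arm, which gives the 300 randomized.

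The sample size is correct and takes no explicit credit for covariates.

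**2. Precision.** Residual SD = 22 × √(1 − R²). Half-width = 1.96 × SD × √(2/120). Power is by noncentral t.

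| Extra R² (assumed) | Residual SD, mm | CI half-width, mm | Power |
|---|---|---|---|
| 0 | 22.0 | 5.57 | 80.1% |
| 0.02 | 21.8 | 5.51 | 80.9% |
| 0.05 | 21.4 | 5.43 | 82.1% |
| 0.10 | 20.9 | 5.28 | 84.1% |

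To relate R² to a grade effect, assume a 50/50 grade split and a Day 5 difference of g mm between grades, so that R² = g² × 0.25 / 22². For g = 5 this is 6.25/484 = 0.013; for g = 10 it is 25/484 = 0.052. The upper end of the table therefore needs a grade effect above 10 mm, or a contribution from time since injury.

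**3. Chance imbalance.** With 120 per arm and a 50/50 split, the SD of the difference in Grade II share is √(2 × 0.25/120) = 0.0645. The 95% range is ±12.7 percentage points. That moves the estimate by at most about 0.6 mm (g = 5) or 1.3 mm (g = 10). In a randomized set this variation is already part of the standard error and is not bias.

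**4. Systematic imbalance in PP.** Shift = grade effect × imbalance. With 5-15 mm and 5-10 percentage points (both assumed), the shift is 0.05 × 5 = 0.25 mm to 0.10 × 15 = 1.5 mm. By normal approximation, starting from 80.4%:

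- Against DDEA 2.32%, power falls to 77.9% (0.25 mm) or 62.9% (1.5 mm).
- In its favor, power rises to 82.8% or 91.7%. The one-sided error at a true difference of 13 mm rises from 2.5% to Φ(−1.96 + 0.25/2.84) = 3.1%, or Φ(−1.96 + 1.5/2.84) = 7.6%.

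These shifts need the grade effect that remains after adjustment for baseline POM. Raw differences between grades would overstate them.

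**The case against.** The strongest reply is that the model already contains the two terms that matter most, the baseline value of the endpoint and the stratification factor, and that anything further is preference. Most of its parts stand.

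- **Validity.** A reader might infer that omitting grade makes the primary analysis invalid. It does not. The ANCOVA is valid without grade.
- **Protection against imbalance.** A reader might infer that the PP arms have no protection against imbalance in severity. The documents do not support that: baseline POM is a severity measure and is in the model. mITT, and ITT with imputation, are also analyzed, which limits post-randomization selection, although with the same covariates. Only severity that baseline POM misses is unadjusted.
- **Prognostic value.** No result in the documents shows that grade predicts Day 5 change beyond baseline POM. The entry criteria also narrow the range. The gain is conditional.
- **Mechanism.** Both arms follow the same blinded four-times-daily schedule, and exclusions are reviewed blind. Nothing in the documents explains why PP exclusions should remove Grade II subjects from one arm more than the other. The possibility remains, but its direction and size are unknown.
- **Time since injury.** It appears only as a 24-hour eligibility check. Nothing visible shows it recorded as an analysis variable.
- **Tabulation.** SAP 4.3.3 does not name grade, but SAP 4.3.1 cites the ankle examination page, and the table references are redacted. Omission from the tables cannot be concluded.

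The reply does not remove the central point. Grade is assessed before randomization, no specified model uses it, and using it costs almost nothing.

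**Conclusion.** The point holds as an optional improvement. The primary ANCOVA adjusts for center and baseline POM but not for sprain grade, and the supportive and imputation models share that omission. There is no error in the model or the sample size.

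On an assumed further R² of 2-10%, power rises by about 1 to 4 percentage points and the half-width narrows by 0.06 to 0.29 mm. On the assumed grade effects and imbalances, adjustment would remove a shift of 0.25-1.5 mm out of the 8 mm between the assumed difference and the margin. Every one of these gains depends on grade adding information beyond baseline POM. If it adds none, little is gained and little is lost.

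**What to change.** Before unblinding:

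1. In protocol 12.2.5 and SAP 4.5.1.2, add sprain grade (I/II) as a factor in the primary ANCOVA, and record the change in SAP section 5.
2. Carry grade into the supportive models in SAP 4.5.1.3 and the imputation model in SAP 4.5.3.
3. Check whether the CRF records the time of injury. Only if it does, add hours from injury to first dose as a covariate in the same models.
4. In SAP 4.3.3, state that grade, and hours if recorded, will be tabulated by arm in PP and mITT.

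The cost is SAP wording and one degree of freedom, or two with hours. No extra subjects or visits are needed, provided the ankle examination page holds grade as a field; that should be confirmed first.

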1.1 Schedule of Activities

The schedule of activities table provides an overview of the subject visits and study procedures.

The investigator may schedule visits (unplanned visits) in addition to those listed on the schedule of activities, in order to conduct evaluations or assessments required to protect the well-being of the subject.

	Screening/Randomization (Baseline)	zation Study Period		
Procedure/Assessment	Visit 1 Day 1	Visit 2 Day 3	Visit 3 Day 5	Visit 4 / Early D/C Day 8 ± 1
Written Informed Consent	X			
Inclusion/Exclusion Criteria	X			
Medical History	X			
Demographics	X			
Current/Prior/Concomitant Medication Review	X	Х	Х	X
Subject Eligibility	X			
Physical Exam / Vital Signs (including height and weight)	x			Xh
Urine Pregnancy Test ^a	X			X
Laboratory Safety Tests	X ^{b,c}			X ^{b,c}
Subject Continued Eligibility		Х	Х	X
Examination of Ankle Sprain	X			
Diagnostic Testing for Ankle	Xd			
Ankle Swelling, Pain on Movement, Tenderness, Ankle Joint Function	x	Х	x	х
Randomization	Х			

GlaxoSmithKline Consumer Healthcare Confidential Template Version Effective: 18-May-18 (CCR #11475)

Page 13 of 64

	Screening/Randomization (Baseline)	Study Period		
Procedure/Assessment	Visit 1 Day 1	Visit 2 Day 3	Visit 3 Day 5	Visit 4 / Early D/C Day 8 ± 1
Adverse Events (AEs) Review	Xg	Х	X	X
Dispense Subject Diary	X	Х	X	
Weigh Study Medication	X	Х	X	X
Dispense Study Medication and Dosing Card	X			
Pain Intensity and Pain Relief (Diary) ^e	X	Х	X	Х
Apply Study Medication at Clinic by trained professional or nurse	x			
Dispense Rescue Medication	X		Xf	
Review Diary		Х	X	X
Count Rescue Medication		Х	X	X
Collect Rescue Medication, Study Medication				X
Collect Diary		Х	X	X
Study Conclusion/Subject Exit from Study				X

Footnotes:

^a Women of child bearing potential

^b Blood samples for chemistry and hematology

^c Review results to ensure that there are no clinically significant abnormalities. Local laboratory will report results to center in order to allow the Investigator to review results no later than 24 hours after blood samples being taken

^d As judged necessary by the investigator to exclude fracture of the ankle

^e Denotes subject completion of diary components

f If necessary

^g Adverse event collection commences from time of signed informed consent

h Height at Visit 1 only

2 INTRODUCTION

Ankle injuries are among the most common sports injuries [Fong 2007]. Eighty-five percent of ankle injuries are sprains, and of these, 85% are inversion sprains of the lateral ligaments [Rimando 2007]. A meta-analysis by Mason et al. of topical non-steroidal anti-inflammatory drugs (NSAIDs) considered sprains, strains and sport injuries, which includes ankle sprain, an appropriate model for acute pain conditions [Mason 2004]. Conventional forms of therapy for acute ankle sprain include use of NSAIDs, cryotherapy with cool packs, elevation of injured extremity, stabilization in a split plaster cast and bandaging [Stöckle 1997].

The efficacy and safety of topical NSAIDs in the treatment of acute, painful musculoskeletal conditions is widely recognized [Vaile 1998, Heyneman 2000, Mason 2004, Rainsford 2008, Zacher 2008]. Over the past 20 years, an increasing number of topical NSAID formulations (diclofenac, ibuprofen, indomethacin, ketoprofen, and naproxen) have been approved. A primary benefit of topically applied NSAIDs is that systemic absorption is only 3-8% of the total systemic absorption achieved with oral administration [Heyneman 2000], limiting the potential for systemic side effects characteristic of NSAIDs. Further advantages of topical delivery include circumventing the gastrointestinal tract and avoiding first-pass metabolism in the liver.

Pharmacokinetic studies have shown that diclofenamic acid, when applied topically, penetrates the skin barrier to reach joints, muscles and synovial fluid, in sufficiently high concentration to exert local therapeutic activity [Rademacher 1991]. The first topical Voltaren formulation, diclofenac diethylamine (DDEA) 1.16% gel (Voltaren Emulgel) has been marketed since 1985 worldwide for the relief of pain and inflammation associated with soft-tissue injuries, soft-tissue rheumatism and osteoarthritis as a three to four times daily application. Several clinical trials have been conducted with DDEA 1.16% gel supporting the efficacy and safety of the topical diclofenac formulation in the soft-tissue injuries, soft-tissue rheumatism, PPD and osteoarthritis indications [Niethard et al 2005, Zacher et al 2001]. Similarly, a 2.32% DDEA gel, which is applied twice daily, has been approved worldwide for the same indications as the 1.16% DDEA gel since 2011. The twice a day topically administered regimen has demonstrated efficacy in relief of acute pain resulting from soft tissue injuries as observed in study [VOPO-P-307][Predel et al 2012]. The global clinical study data in conjunction with the extensive post marketing experience, provide robust evidence of the safety and efficacy of both the marketed DDEA gel formulations.

2.1 Study Rationale

Topical diclofenac products are well established globally for the treatment of pain and inflammation due to acute trauma as well as for the relief of pain associated with non-serious osteoarthritis (OA) of the peripheral joints e.g. knee and fingers. The originator product DDEA 1.16% gel (Voltarol Emulgel in the UK, and generic name of DDEA Emulgel was registered in China) was first registered in 1985 in Switzerland and Romania for use at a dose of 2-4 g applied three to four times daily and is currently registered in over 130 countries of which over 80 countries market this product as over-the-counter (OTC).

Topically administered 2.32% DDEA gel for use at a dose of 2-4 g applied twice daily (b.i.d.) was first approved in 2011 in Portugal as a line extension to DDEA 1.16% gel and is now registered in 72 countries and is marketed in 42 countries.

As part of the global expansion for the product, China has been identified as a desirable market for registration of DDEA 2.32% gel. The identified registration pathway for the DDEA 2.32% gel is variation specifying addition of a new strength to the already registered DDEA 1.16% gel (License Number H20181225/H20181226, firstly issued on March 12, 2013), with the same indications

GlaxoSmithKline Consumer Healthcare Confidential Template Version Effective: 18-May-18 (CCR #11475) Page 15 of 64

Diclofenac Diethylamine 2.32% Study 211206 Protocol Amendment 1

as currently registered for DDEA 1.16% gel, i.e. for the relief of mild to moderate pain in muscles, soft tissues, and joints, e.g. muscles or soft tissue pains caused by sprain, pulling injury, contusions, strain, waist-back injury and various arthralgia etc, and for symptomatic treatment of osteoarthritis.

In support of the proposed registration, the National Medical Products Administration (NMPA) approved a clinical trial application (CTA) on November 06, 2016 (CTA No. 2016L09875). The approved CTA stipulated that a non-inferiority study assessing the efficacy and safety of the DDEA 2.32% versus that of the registered DDEA 1.16% should be conducted in a local population.

To this effect, GSKCH intends to conduct a randomized, double blind, multi-center, active controlled, parallel group, non-inferiority study to evaluate the efficacy and safety of DDEA 2.32% gel applied twice daily versus DDEA 1.16% gel applied four times daily in subjects with ankle sprain in China.

Ankle sprain is a common and well defined joint injury involving the soft tissues. A significant proportion of subjects experience strong pain and functional impairment without appropriate treatment options. The DDEA 2.32% gel offers the opportunity to provide a safe and effective treatment while improving subject treatment compliance and convenience.

Complete information for this compound may be found in the single reference safety document (SRSD), which for this study is the Investigator's Brochure.

